dietary education for IBS, including a low FODMAP diet, or previously received antibiotics, including rifaximin, for treatment of IBS-D or SIBO will be excluded from the study.

GI Symptom Assessment: All IBS-D subjects will complete validated questionnaires to quantify severity of IBS symptoms, including IBS Symptom Severity Scale (IBS-SSS), Gastrointestinal Symptom Rating Scale-IBS (GSRS-IBS), an 11-point numerical rating scale (NRS) for abdominal pain and bloating, and Bristol Stool Form Scale (BSFS) at baseline (55–58). The NRS for abdominal pain and bloating and the BSFS will be completed online through the REDCap Survey Tool.

Psychological and Quality of Life Assessment: IBS-D subjects will also complete validated questionnaires to assess for presence of and to measure severity of psychological disorders, GI specific anxiety, and impairments in quality of life. All IBS-D subjects will complete the Patient Health Questionnaire (PHQ-9), Visceral Sensitivity Index (VSI), and IBS-quality of life (IBS-QOL) (59–61). The PHQ-9 will be reviewed by the study team within 24 hours of completing the questionnaire. If a subject answers affirmative to the question “Thoughts that you would be better off dead or of hurting yourself in some way,” they will be provided with the appropriate referral to mental health counseling and/or the subject’s PCP will be alerted.

Dietary Assessment: All IBS-D subjects will undergo initial consultation with the study team and will be instructed on how to monitor and record their dietary intake. IBS-D subjects will then record daily their dietary intake for 3 days prior to fecal collection.

Fecal Collection and Preparation: Three fresh stool samples will be collected from all IBS-D subjects at baseline. Each sample will be immediately placed into an OMNIgene•GUT collection tube (DNA Genotek, Inc., Ottawa, ON, Canada) which allows for self-collection and stabilization of fecal DNA samples for up to 60 days at ambient temperature (62). Samples will then be mailed back or picked up by the study team and stored at -80°C in [name]’s Lab for long-term storage. If patients consent to the optional portion of the study, they will provide a stool sample in 95% ethanol at Visits 1, 3, 4, and 5. We will also collect a one-time stool sample and symptom questionnaires from healthy controls. Healthy controls will not have a history of gastrointestinal conditions and do not report any abnormal bowel movements or abdominal pain.

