We will prospectively follow the results of GHBT and fecal microbiota before and after treatment with rifaximin and low FODMAP dietary restriction. We will collect fecal samples throughout the study period in IBS-D patients. All IBS-D subjects will also undergo GHBT before and after

intervention. The primary aim will be change in fecal microbial diversity after intervention with rifaximin or low FODMAP diet compared with baseline. Secondary outcomes will evaluate whether response to treatment with rifaximin or low FODMAP diet is associated with: (i) presence of SIBO on initial testing, (ii) persistence of SIBO after intervention, (iii) changes in α - and β - diversity as well as in dominant phyla. We will also utilize human intestinal enteroids to model how host-microbial interactions may influence response to treatment with rifaximin or low FODMAP diet in IBS.

2B. Experimental Methods:

Fecal Collection and Preparation: Stool samples will be collected from all IBS-D subjects at weeks 2, 4 and 5 as described in Aim 1. Stool samples will be stored for up to 5 years at the conclusion of the study for future analyses, including evaluating differences in metabolomics, such as histamine, p-hydroxybenzoic acid, azelaic acid, and H₂ (45). This portion of the study is optional, and subjects have a choice to allow their stool samples to be stored for this sub-study. This may provide mechanistic descriptions of how changes in gut microbiota lead to changes seen in IBS. If patients consent to this optional portion of the study, they will provide a stool sample in 95% ethanol at weeks 0, 2, 4, and 5. Subjects will be compensated a nominal amount of \$20 for stool samples returned at week 0 and \$10 each for weeks 2, 4 and 5 to express our gratitude for their participation in the study. We will also provide mailers to mail back samples to minimize study burden on participants.

GHBT: Glucose H₂/CH₄ test will be repeated at week 5 as described in Aim 1.

Serum cytokine profiles: Serum cytokines will be repeated at week 5 as described in Aim 1. Handling and processing of the blood will be described in Appendix 1.

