We will develop and validate a predictive model of response to low FODMAP diet using data from the subjects randomized to a low FODMAP diet (Aim 1) combined with existing data from a separate cohort of IBS-D subjects previously treated with a low FODMAP diet (HUM 00053274).

3B. Experimental Methods:

We will use the combined cohort of patients treated with a low FODMAP diet (Aim 1 and HUM #00053274), which will be split into a training set from a random sample of 80% of the data while the remaining 20% of the data will serve as the test set. Using a random forest model, 5x2 nested cross-validation (CV) will be performed within the training set for model selection and hyperparameter tuning. The candidate models will be compared by testing for overlap of confidence intervals for area under the curves (AUCs, two-sided test). Once a final model is selected, model performance will be evaluated on the test set.

Study Timeline:

Figure 1 IBS Subject Timeline

Schedule of Events - Low FODMAP Group

Visit Number	Pre-Visit	Visit 1	Visit 2	Visit 3	Visit 4	Visit 5
Visit Description	Pre-screening (Phone/in person)	Baseline (Phone/in person)	Monitoring (Phone/in person)	Monitoring (Phone/in person)	Monitoring (Phone/in person)	Monitoring/Outcomes (Phone/in person)
Time point	Eligibility	Day 0	Day 7±3 days	Day 14±3 days	Day 28±3 days	Day 35±3 days
7 day pre-screening questionnaire	X					
Informed Consent	X					
Medical History /Physical Examination		X	X	X	X	X
Urine pregnancy test (Females of childbearing age)		X				
Washout	X					
Questionnaires		X		X		X

3-day food diary		X				
24-hour dietary recall			X	X	X	X
GI nutrition consultation		X		X		
Colonoscopy with mucosal biopsies (optional)	X					
Serum Cytokine Profiles (optional)		X				X
Buccal swab collection (optional)		X				
Glucose hydrogen breath testing		X				X
Stool collection for fecal microbial analysis		X (3 baseline samples)		X	X	X
Randomization	X					
Dietary Compliance			X	X	X	X
Adverse Events Monitoring			X	X	X	X

*Female participants capable of bearing children will be required to attend visit 1 in person for the pregnancy test

*During COVID-19 pandemic, all hydrogen breath tests will be conducted remotely

Schedule of Events – Rifaximin Group

*Female participants capable of bearing children will be required to attend visit 1 in person for the pregnancy test

*During COVID-19 pandemic, all hydrogen breath tests will be conducted remotely

Visit Number	Pre-Visit	Visit 1	Visit 2	Visit 3	Visit 4	Visit 5

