10 STATISTICAL CONSIDERATIONS

Aim 1:

All of the interventional analyses will be analyzed on an intention-to-treat basis. Each IBS-D subject will act as his/her own control for analysis of the effects of either rifaximin or low FODMAP diet intervention. This paired design inherently eliminates a significant amount of bias/confounding and affords increased statistical power. We will power our study to detect a $\geq 30\%$ improvement in mean daily bloating or abdominal pain after intervention compared with baseline. Using available data from a US study on low FODMAP diet in IBS patients (42), we conservatively estimate that we will require 14 IBS-D subjects in each arm to have $>90\%$ power to detect a mean difference of 1.7 in abdominal bloating scores after intervention via paired t-tests with the expected standard deviation (SD) of ± 1.8 . Thus, our expected enrollment of 32 IBS-D subjects in each arm will be more than sufficient for analyzing this aim (see biostatistical analysis for Aim 2), even if the SD is nearly two-fold larger than expected.

Aim 2:

We will examine both inter- and intra-individual variability in microbiota-derived metrics. We plan to use a paired design to eliminate a significant amount of bias/confounding and increase statistical power. We anticipate that there will be some variability in the three samples collected prior to treatment, and various techniques will be employed to average these data so they are incorporated as the baseline. For example, for α diversity (Shannon index) a simple average of the three time points will be sufficient to

establish a baseline α diversity. Similar techniques will be applied to other community structure metrics, to create “deltas” between post-treatment time points and the baseline.

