These microbe-derived metrics and accompanying clinical variables will be initially analyzed through descriptive statistics before/after intervention. Histograms and measures of frequency or central tendency/spread will be used to optimize variable constructions. Subsequently, initial bivariable longitudinal analyses in an inter-individual fashion (assessing group-wide trends before/after intervention) that also account for the paired nature of the data (intra-individual) will be employed for categorical data (McNemar’s test) and continuous data (paired t-test), or their non-parametric equivalents for data not normally distributed. Multiple comparisons will be made for individual OTU abundance metrics, with a focus on the most abundant taxa. However, we will avoid a high false discovery rate through use of linear discriminant analysis effect size (LEfSe) analysis (70). Similar to Aim 1, we will power our study using a paired t-test based on the primary outcome to detect a change in diversity at the end of the intervention compared with baseline. In addition, we will also examine intermediate endpoints or longitudinal trends over time to determine if these are important. If this is the case, we will also use mixed model analyses with repeated measures.

Although this work is exploratory, we wanted to ensure that we will have sufficient power to detect notable differences in microbial and functional characteristics with our planned recruitment base. Based on prior studies with low FODMAP diet in IBS patients (42,45,71), we conservatively estimate that 60% of IBS-D subjects will respond to treatment. We further expect that only those IBS-D subjects who respond to a low FODMAP diet will show changes in fecal microbial diversity. Given our sample size of 32 subjects per arm, we will have >90% power to detect a mean difference ≥ 0.4 in θ_{YC} (a measure of β -diversity) between responders and non-responders. As we are already seeing differences in θ_{YC} of this magnitude or greater, this suggests we are appropriately powered to detect meaningful differences in the microbiota between groups even if our standard deviation is 2-fold greater than expected.

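### Aim 2: a raw mean of three baseline stools tested by signed-rank against one post-treatment stool leans towards false depletion of skewed taxa; the plan leaves this route open

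*Combined protocol and SAP*

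**What the plan says.** Section 6, Aim 1 (fecal collection): "Three fresh stool samples will be collected from all IBS-D subjects at baseline". Section 6, Aim 2: "Stool samples will be collected from all IBS-D subjects at weeks 2, 4 and 5 as described in Aim 1". Both schedules of events mark three samples at Visit 1 and a plain X at Visits 3, 4 and 5, which I read as one stool per visit. No averaging of post-treatment stools is planned.

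Section 10, Aim 2 anticipates "some variability in the three samples collected prior to treatment, and various techniques will be employed to average these data", the result serving as the baseline. A simple average is named only for the Shannon index, as an example. The section continues: "Similar techniques will be applied to other community structure metrics", in order to form differences between each post-treatment time point and baseline.

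Before/after comparisons of continuous data use the paired t-test, "or their non-parametric equivalents for data not normally distributed". On taxa: "Multiple comparisons will be made for individual OTU abundance metrics", with LEfSe named as the means of avoiding a high false discovery rate. The section also says that histograms and measures of spread will guide how variables are constructed. It names no averaging scale for taxa, no transformation and no specific rank test.

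**The concern.** The signed-rank test, the usual non-parametric counterpart of the paired t-test, needs differences that are symmetric about zero when there is no effect. One right-skewed value minus the mean of three such values is not symmetric. The mean of three is pulled up by occasional high values and so has a higher median than a single value. The later stool therefore falls below its own baseline mean in more than half of subjects, even when all four stools come from one unchanged distribution.

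The error has a direction. In the rifaximin arm a spurious fall in a taxon would look like an antibiotic effect. In the diet arm it would look like the harm to microbial composition that section 3 raises as a theoretical concern. A correction across taxa does not help if each single-taxon p-value is already too small.

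**Working it through.** **The plan's own figures.** The documents state no false-positive rate for taxon tests and no significance level. The level can be inferred from Aim 1: a paired t-test with difference 1.7, SD 1.8 and n = 14 has power 0.904 at two-sided 5% (0.878 at n = 13). This reproduces the stated 14 per arm with more than 90% power, so I use two-sided 5%.

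**Inputs from the documents.** Three baseline stools; one stool at each later time point; 200 subjects randomised 1:1, so 200/2 = 100 per arm (section 6); 32 per arm in section 10. The two sample sizes conflict, which is a separate matter, so both are shown.

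**Assumed.** Abundance of stool j in subject i is X_ij = exp(m_i + e_ij), with m_i ~ N(0, 1) and e_ij ~ N(0, s²). The four stools are exchangeable, meaning no treatment effect. The within-person log SD s is not in the documents, so a range is shown.

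**Quantity tested.** d_i = X_i4 − (X_i1 + X_i2 + X_i3)/3, by signed-rank.

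| Within-person log SD | 0.5 | 0.75 | 1.0 | 1.5 |
|---|---|---|---|---|
| Rejections, 32 per arm | 7% | 11% | 14% | 21% |
| Rejections, 100 per arm | 11% | 22% | 31% | 49% |

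- The probability that the later stool lies below the baseline mean runs from 56% to 63% over this range.
- About 90% or more of the rejections are falls. The like-for-like nominal rate for falls is 5%/2 = 2.5%.
- Varying the between-person log SD from 0 to 2 gives, at 100 per arm, 11-14% (s = 0.5) to 49-53% (s = 1.5), and at 32 per arm 7-8% to 18-23%.
- Monte Carlo standard error with 2,000 replicates is √(0.11 × 0.89/2000) = 0.7 percentage points at 11%.
- At s = 0.25 and 100 per arm the rate is about 6%.
- With Poisson read counts (assumed depth 10,000, mean abundance 0.05-1%, s = 0.75-1.0) the rate is about 15-30% at 100 per arm.

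**Illustration.** Of 50 unchanged taxa (my number) at s = 0.75-1.0, expected rejections are 50 × 0.22 to 50 × 0.31 = 11 to 15.5 at 100 per arm, and 50 × 0.11 to 50 × 0.14 = 5.5 to 7 at 32 per arm. Expected nominal falls are 50 × 0.025 = 1.25.

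**Where the problem does not bite.** The paired t-test on the same raw differences stays at about 2-7%. Signed-rank on a normally distributed index gives 4.6%. A left-skewed, Shannon-like example gives 7.6%, mostly false rises. An inverse Simpson index with log SD 0.3-0.4 gives about 8-9%.

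**Candidate repairs, no effect present.**

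| Method | Rejections |
|---|---|
| Within-subject permutation of the post-treatment label | about 3-6% in every setting, zeros included |
| Log-scale mean of three against one, signed-rank, no excess zeros | about 5-6% at 100 per arm |
| The same with a pseudocount and 10-20% excess zeros per stool (assumed) | about 14-33%, mostly false rises |
| Median of three against one | signed-rank 6-10%, paired t-test 9-24%, towards rises |

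**The case against.** The strongest reply is that the plan does not commit to the procedure simulated here. Taxa are not named in the averaging sentences, the averaging technique is left open, signed-rank is never named, and variable construction is to be guided by the observed distributions, which leaves room for a log scale. Taxon comparisons are assigned to LEfSe. The work is called exploratory, and the Aim 2 primary is powered on a paired t-test.

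Much of this stands. A reader might infer that the plan's taxon tests will show false depletion at 11-49%. The documents do not support that. The range depends on an assumed within-person SD, on raw averaging, on signed-rank, and on 100 per arm when section 10 works with 32. Nor may one infer that the primary result is compromised.

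Two parts of the reply do not remove the point. First, a simple average is the only technique named and similar ones are to follow, so raw averaging with a rank fallback is a natural reading of the text. Second, LEfSe cannot be credited as protection without knowing how it would use the pairing and the averaged baseline. If it were run as an unpaired rank comparison (an assumption), null rejection at 100 per arm ranged from 0% to 73%, depending on the within-person spread.

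**Conclusion.** The point holds conditionally. Section 10 permits, and most naturally suggests, an analysis of skewed metrics whose null rejection rate is about 7-21% at 32 per arm or 11-50% at 100 per arm, nearly all as falls. This rests on log-normal abundances, within-person log SD of 0.5 to 1.5, raw-scale averaging, signed-rank and a two-sided 5% level. It shrinks to almost nothing at log SD 0.25 and grows with sample size. It concerns taxon-level results and, slightly, skewed indices such as inverse Simpson; the diversity primary by paired t-test is little affected. It should be corrected before analysis because the choice of averaging scale and test decides whether the error is near 5% or several times that.

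**What to change.** In section 10, Aim 2, state that:

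- for individual taxa and other skewed metrics, the before/after p-value comes from a within-subject permutation of which of the four stools (three baseline, one at the time point analysed) is labelled post-treatment;
- signed-rank is not applied to a three-stool mean against a single stool;
- each stool may be put on a log or centred log-ratio scale before averaging, for effect estimates. Log averaging with a pseudocount followed by signed-rank is not to be relied on for taxa with many zeros, where it can produce false rises;
- if LEfSe is kept, how it handles the pairing and the averaged baseline is described.

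The permutation works on the raw or log scale and with zeros. It assumes that a subject's four stools are exchangeable when treatment does nothing, as the simulations here do. The cost is a few sentences, a few lines of code and slightly more computation. No samples or patients are added. If the log scale is used, effects are reported as ratios.

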11 REGULATORY REQUIREMENTS

11.1 Informed Consent ¹

¹ The IRB may waive some or all elements of informed consent – consult the IRB for consenting requirements.

Informed consent will be signed by subjects after the protocol is explained by either the PI, co-I or study coordinator. If an IBS-D subject is a patient of the PI or Co-I, the study coordinator will be responsible for obtaining informed consent to avoid potential issues of coercion. Before signing, IBS-D subjects will be given ample opportunity to ask questions about the protocol. Consent forms could be signed in the Taubman Center or in the GI Physiology Laboratory in the Medical Procedures Unit. Please see Informed Consent attached as an appendix.

11.2 Subject Confidentiality

All study team members will make every effort to protect each IBS-D subject's confidentiality. Participants will have privacy in a closed exam room to be able to provide information to the PI and/or study coordinator regarding medical history, current condition, and any other relevant information pertaining to the study. Research records, data, and/or specimens will be kept in a locked office and/or locked cabinet with access restricted only to study team members. Study members will also secure electronic data on computers by using password protection, installing and regularly updating security software, as well as encryption of data. Only the PI and the Study Coordinator will have access to the data and IBS-D subject identifiers. Subjects will receive REDCap encrypted and secure links to fill out the online questionnaires. Only the PI and the Study Coordinator will be allowed to enter data onto the password-protected web-based server. Patients will be called using University Health System phones to protect patient privacy.

11.3 Data Safety Monitoring Plan

11.3.1. Oversight Responsibilities

Oversight of the trial is provided by the Principal Investigator (PI), [name]. [name] assures that informed consent is obtained prior to performing any research procedures, that all subjects meet eligibility criteria, and that the study is conducted according to the IRB-approved research plan.

11.3.2 Unanticipated Problems, Adverse Events and Serious Adverse Event Collection and Reporting²

² The Office for Human Research Protections (OHRP) considers unanticipated problems involving risks to subjects or others to include, in general, any incident, experience, or outcome that meets **all** of the following criteria:

There is minimal direct risk to study subjects as all interventions are well accepted treatments for IBS. All members of the study team will stay current with training in the protection of human research participants and HIPAA. The PI will regularly monitor the data in collaboration with the research team, with periodic review by the IRB at the University of Michigan. We will minimize risk by using rigorous data security protocols to protect protocol deviations (e.g. violation of human subject confidentiality or comprised data integrity) and will ensure expedient reporting to the IRB (see below).

All adverse clinical experiences, whether observed by the investigator or reported by the subject, must be recorded, with details about the duration and intensity of each episode, any actions taken, and the subject's outcome. The Principal Investigator must evaluate each adverse experience for its relationship to the study and for its seriousness.

The Principal Investigator must appraise all abnormal laboratory results for their clinical significance. If any abnormal laboratory result is considered clinically significant, the Principal Investigator must provide details about the action taken and about the subject's outcome.

All AEs will be assessed by the Investigator(s) and will be recorded in the eCRF, including the date of onset and resolution, severity, relationship to study, outcome, and action taken. All AEs will be reported to the IRB that meet reporting criteria. Toxicity will be graded according to the Common Toxicity Criteria as follows:

0 = No adverse event or within normal limits

1 = Mild AE, not requiring treatment

2 = Moderate AE, resolved with treatment

3 = Severe AE, resulted in inability to carry on normal activities and required professional medical attention

4 = Life threatening or disabling AE

- unexpected (in terms of nature, severity, or frequency) given (a) the research procedures that are described in the protocol-related documents, such as the IRB-approved research protocol and informed consent document; and (b) the characteristics of the subject population being studied;
- related or possibly related to participation in the research (in the guidance document, possibly related means there is a reasonable possibility that the incident, experience, or outcome may have been caused by the procedures involved in the research); and
- suggests that the research places subjects or others at a greater risk of harm (including physical, psychological, economic, or social harm) than was previously known or recognized.

An incident, experience, or outcome that meets the three criteria above generally will warrant consideration of substantive changes in order to protect the safety, welfare, or rights of subjects or others.

5 = Fatal AE

Serious adverse event (SAE) is defined by the FDA as an AE resulting in any of the following outcomes: Death, a life-threatening adverse event, inpatient hospitalization or prolongation of existing hospitalization, a persistent or significant incapacity or substantial disruption of the ability to conduct normal life functions, or a congenital anomaly/birth defect. Important medical events that may not result in death, be life-threatening, or require hospitalization may be considered serious when, based upon appropriate medical judgment, they may jeopardize the patient or subject and may require medical or surgical intervention to prevent one of the outcomes listed in this definition. Once an AE or SAE is known, research team members at the study site will ensure that participants receive appropriate care and all actions taken by the PI and/or co-investigator after observing the AE or SAE will be documented.

